### 5.3.3.2.1 TEAEs – Overview

An overall summary table will be provided showing the number of TEAEs, the number, and proportion of subjects who presented:

- Any TEAE.
- Any TEAE grade 3 or higher.
- Any TEAE grade 3.
- Any TEAE grade 4.
- Any TEAE grade 5.
- Any TEAE related to APX005M.
- Any TEAE related to APX005M grade 3 or higher.
- Any TEAE related to APX005M grade 3.
- Any TEAE related to APX005M grade 4.
- Any TEAE related to APX005M grade 5.
- Any TEAE related to APX005M only
- Any TEAE leading to dose reduction (APX005M).
- Any TEAE leading to dose delay (APX005M)
- Any TEAE leading to treatment interruption (APX005M)
- Any TEAE leading to treatment discontinuation (APX005M).
- Any TEAE related to Radiotherapy (applicable to Cohort 3)
- Any TEAE related to Radiotherapy only (applicable to Cohort 3)
- Any TEAE leading to radiation discontinuation (only applicable in Cohort 3)
- Any TEAE Immune Mediated.
- Any TEAE Infusion reaction/ cytokine release syndrome.
- Any Serious TEAE.
- Any Serious TEAE with a fatal outcome.
- Any Serious TEAE related to APX005M.
- Any Serious TEAE related to APX005M with fatal outcome.
- Any Serious TEAE related to APX005M only
- Any Serious TEAE related to Radiotherapy (applicable to Cohort 3)
- Any Serious TEAE related to Radiotherapy only (applicable to Cohort 3)

This information will be presented by cohort and overall.

Separate listings will be produced for:

- TEAEs
- TEAEs excluding events marked as a symptom of CRS/IRR
- Serious TEAEs
- TEAEs leading to APX005M discontinuation
- TEAEs leading to APX005M delay
- TEAEs leading to APX005M reductions
- TEAEs leading to infusion interruption
- TEAEs with fatal outcome
- TEAEs immune-mediated events
- TEAEs marked as a symptom of CRS / IRR

The listings will be sorted by Subject ID.

### 5.3.3.2.2 TEAEs.

Treatment Emergent Adverse Events will be summarized in different approaches:

- By worst grade according to National Cancer Institute Common Terminology Criteria for Adverse Events (NCI-CTAE version 4.03) per subject, using the latest version of MedDRA as event category.

When calculating the incidence of TEAEs by grade each subject will only be counted once (corresponding to the maximum toxicity grade), and any repetitions of adverse events will be ignored; the denominator will be the corresponding total Safety population Overall.

- By cohort

When calculating the incidence of TEAEs by cohort each subject will only be counted once, and any repetitions of adverse events will be ignored; the denominator will be the corresponding total Safety population Overall.

The following tables will be created:

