### 5.3 Summary of Statistical Methods

All subjects entered in the database will be included in subject data listings. The listings will be generally sorted by cohort and then Subject ID unless specified otherwise. All relevant subject data will be included in listings.

All applicable data will be summarized by cohort unless specified otherwise. In addition, data will be summarized by visit and/or time-point when appropriate. Unscheduled or repeat assessments will not be included in summary tables but will be included in listings.

Continuous variables will be summarized using the number of observations (n), the number of subjects with non-missing values, mean, standard deviation (SD), median, Q1, Q3, minimum, and maximum along with the total number of subjects contributing values.

Descriptive statistics for categorical/qualitative data will include frequency counts and percentages. The total number of subjects in the cohort (N) will be used as the denominator for percent calculations unless stated otherwise in the table footnote.

Time to event distributions (eg, PFS and DoR) will be estimated using the Kaplan-Meier methodology. In these analyses, in addition to the Kaplan-Meier curve, the median, Q1, Q3, and their corresponding CI 90% (if estimable), the number of events and censored cases distribution will be shown.

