#### TEAEs: Worst grade by subject (by cohort):

- Incidence of TEAEs will be tabulated by Primary System Organ Class (SOC), Preferred Term (PT) and maximum CTCAE grade, showing the total incidence of SOC and PT within SOC. A table will be included for each cohort.
- Incidence of TEAEs will be tabulated by Preferred Term (PT) and maximum CTCAE grade, in order of highest number of subjects. A table will be included for each cohort.

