### **TEAEs: Worst grade by subject related to Radiotherapy (only cohort 3)**

- Incidence of TEAEs related to radiotherapy will be tabulated by SOC, PT and maximum CTCAE grade, showing the total incidence of SOC and PT within SOC.
- Incidence of TEAEs related to radiotherapy will be tabulated by PT, and maximum CTCAE grade, in order of highest number of subjects.

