### **TEAEs: Worst grade by subject Immune mediated:**

- Incidence of TEAEs immune mediated will be tabulated by SOC, PT and maximum CTCAE grade, showing the total incidence of SOC and PT within SOC.
- Incidence of TEAEs immune mediated will be tabulated by PT and maximum CTCAE grade, in order of highest number of subjects.

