### **TEAEs: Worst grade by subject of symptoms that compromise an APX005M Infusion reaction and/or cytokine release syndrome:**

- Incidence of TEAEs considered symptoms that compromise an APX005M infusion reaction and/or cytokine release syndrome will be tabulated by SOC, PT and maximum CTCAE grade, showing the total incidence of SOC and PT within SOC.
- Incidence of TEAEs considered symptoms that compromise an APX005M infusion reaction and/or cytokine release syndrome will be tabulated by PT and maximum CTCAE grade, in order of highest number of subjects.

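### SAP 5.3.3.2.2 gives by-cohort adverse event incidence an overall safety denominator, against the cohort-N rule in SAP 5.3; read literally, at planned N, cohort percentages shrink 3.6-fold (Cohorts 1 and 2) and 2.2-fold (Cohort 3)

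*SAP*

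**What the plan says.** SAP 5.3.3.2.2 describes two ways of summarising TEAEs, by worst grade and by cohort, and ends both with the same denominator sentence. For the second it reads: "When calculating the incidence of TEAEs by cohort each subject will only be counted once", repeats are ignored, and "the denominator will be the corresponding total Safety population Overall".

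SAP 5.3 gives the general rule: "The total number of subjects in the cohort (N) will be used as the denominator for percent calculations". The only exception it allows is one stated in a table footnote.

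The tables listed after 5.3.3.2.2 are mostly cohort-specific. For the worst-grade, grade 3 or higher, and APX005M-related tables the SAP says "A table will be included for each cohort". The tables for discontinuation, serious and fatal events are headed as by cohort. For Cohort 3 only, "Incidence of TEAEs related to radiotherapy will be tabulated by SOC, PT and maximum CTCAE grade".

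The overview table in SAP 5.3.3.2.1 names no denominator of its own and says "This information will be presented by cohort and overall", so the general cohort-N rule applies to it.

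**The concern.** A percentage labelled as incidence in a cohort should have that cohort's treated subjects as its denominator. The sentence in 5.3.3.2.2 names the whole Safety population instead, under a bullet headed as by cohort. Both rules cannot govern the same column.

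Safety in each cohort is a secondary objective (SAP 2.2.2), and SAP 5.3.3 says safety is assessed by cohort. If the literal rule were programmed:

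- Cohort percentages by system organ class and preferred term would be too low for all TEAEs and for grade 3 or higher, related, radiotherapy-related, serious and fatal events.
- The detailed tables would disagree with the overview table in the same report.
- Cohorts of different size could not be compared on the printed percentages, because each would be scaled by its share of the total. Cohort 3, the radiotherapy cohort, would look worse than Cohorts 1 and 2 at equal true incidence.

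**Working it through.** **Inputs.** Planned sizes from SAP 5.1 (and protocol 6.1): 11 in Cohort 1, 11 in Cohort 2, 18 in Cohort 3. Safety population from SAP 3.2: everyone given any APX005M. The documents give no actual Safety-population counts and no TEAE percentages.

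**Reproducing the plan's own figures.** The only figures the plan computes from these sizes are the standard errors of the response rate, SE = √(p(1−p)/n):

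- 2/11: √(0.1818 × 0.8182 / 11) = 0.1163, against the stated 11.6%.
- 3/18: √(0.1667 × 0.8333 / 18) = 0.0878, against the stated 8.8%.

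Both agree, which confirms 11, 11 and 18 as the planned sizes.

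**Shrinkage under the literal rule.** If x subjects in a cohort of size n have the event and the total is N, the cohort incidence is x/n and the printed figure is x/N. The true incidence is therefore divided by N/n. With N = 11 + 11 + 18 = 40:

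- Cohorts 1 and 2: 40/11 = 3.64
- Cohort 3: 40/18 = 2.22

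| Case | Cohort N | Overall N |
|---|---|---|
| Event in 5 of 11, Cohort 1 or 2 | 5/11 = 45.5% | 5/40 = 12.5% |
| Radiotherapy-related event in 9 of 18, Cohort 3 | 9/18 = 50.0% | 9/40 = 22.5% |
| Event in every subject, Cohort 1 or 2 | 11/11 = 100% | 11/40 = 27.5% |
| Event in every subject, Cohort 3 | 18/18 = 100% | 18/40 = 45.0% |

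The last two rows show the distortion between cohorts: equal incidence looks 45.0/27.5 = 18/11 = 1.64 times higher in Cohort 3. In the radiotherapy row, 22 of the 40 subjects in the denominator belong to cohorts that receive no study radiotherapy.

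**If the actual Safety-population counts differ from plan.** Subjects who were treated but not evaluable for response could be replaced (SAP 2.3.5), yet they stay in the Safety population. As an assumed range, take 9 to 14 treated in each of Cohorts 1 and 2 and 15 to 22 in Cohort 3:

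- Cohort 1 or 2: from (14 + 9 + 15)/14 = 38/14 = 2.7 to (9 + 14 + 22)/9 = 45/9 = 5.0
- Cohort 3: from (9 + 9 + 22)/22 = 40/22 = 1.8 to (14 + 14 + 15)/15 = 43/15 = 2.9

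The shrinkage is material throughout.

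**Which tables are touched.** The conflict reaches the cohort columns and cohort-specific tables listed after 5.3.3.2.2. It does not reach subject counts, listings or the overview table. Two sets of tables state no cohort split: "Incidence of TEAEs immune mediated will be tabulated by SOC, PT and maximum CTCAE grade", and "Incidence of TEAEs considered symptoms that compromise an APX005M infusion reaction and/or cytokine release syndrome" likewise. If those are pooled across cohorts, the total N is right for them.

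**The case against.** The strongest reply is that the literal reading is not what was meant. If one fixed total served every column, *corresponding* would have nothing to refer to; it makes sense if it means the Safety total for the column or table shown. SAP 3.2 analyses subjects in the treatment group they received, and SAP 5.3, 5.3.3 and the one-table-per-cohort layout all point to cohort N. The shells, held in an external file (SAP 7), may already be right. The study is exploratory, these percentages feed no test or stopping rule, and a reader with the counts and cohort sizes could recalculate them.

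Much of this stands. It shows that cohort N was probably intended, and that the shrinkage factors describe what follows if the sentence is obeyed, not what is certain to appear. It does not remove the conflict. The benign reading leaves *Overall* without meaning under a by-cohort bullet, and a specific section is normally taken to override a general one, so a programmer could reasonably follow it. Where the SAP wants another denominator, as for disposition in 5.2, it names it plainly.

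Two limits should be kept in view. Cohorts 1 and 2 remain comparable with each other only if their actual Safety-population counts are equal, as planned; separate replacement in each cohort could make them differ. The missing cohort layout for the immune-mediated and cytokine-release tables is a related gap, not evidence of the wrong denominator.

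**Conclusion.** The concern holds. SAP 5.3.3.2.2 as written conflicts with SAP 5.3 and with the by-cohort safety objective, and following it would print cohort incidences that are wrong and disagree with the overview table. The factors of 3.6 and 2.2 rest on the literal reading and on the planned 11, 11 and 18 all being treated; the assumed range above gives 2.7 to 5.0 for Cohorts 1 and 2 and 1.8 to 2.9 for Cohort 3. That the text supports two denominators is certain. Whether the tables would come out wrong cannot be judged without the shells. This should be fixed before the tables are produced.

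**What to change.** Replace the denominator sentence in both bullets of SAP 5.3.3.2.2 with a rule to this effect: for cohort columns and cohort-specific tables, including the Cohort 3 radiotherapy tables, the denominator is the number of Safety-population subjects in that cohort; the total Safety-population N is used only for overall columns and for tables pooled across cohorts.

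State also whether the immune-mediated tables and the tables of infusion-reaction and cytokine-release symptoms are pooled or by cohort, so that their denominator follows from the same rule. Then check the denominators and footnotes in the table shells against the corrected text.

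The cost is a short SAP edit and a shell check. No new data are needed, and neither study conduct nor the primary endpoint is affected.

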#### TEAEs: by cohort:

- Incidence of TEAEs will be tabulated by Primary System Organ Class (SOC) and Preferred Term (PT), showing the total incidence of SOC and PT within SOC.
- Incidence of TEAEs will be tabulated by Preferred Term (PT), in order of highest number of subjects.

#### TEAEs: Worst grade by subject (by cohort):

- Incidence of TEAEs will be tabulated by Primary System Organ Class (SOC), Preferred Term (PT) and maximum CTCAE grade, showing the total incidence of SOC and PT within SOC. A table will be included for each cohort.
- Incidence of TEAEs will be tabulated by Preferred Term (PT) and maximum CTCAE grade, in order of highest number of subjects. A table will be included for each cohort.

#### TEAEs: Worst grade by subject grade 3 or higher (by cohort):

- Incidence of TEAEs grade 3 or higher will be tabulated by SOC, PT and maximum CTCAE grade, showing the total incidence of SOC and PT within SOC. A table will be included for each cohort.
- Incidence of TEAEs grade 3 or higher will be tabulated by PT and maximum CTCAE grade, in order of highest number of subjects. A table will be included for each cohort.

#### TEAEs: Worst grade by subject related to APX005M (by cohort):

- Incidence of TEAEs related to APX005M will be tabulated by SOC, PT and maximum CTCAE grade, showing the total incidence of SOC and PT within SOC. A table will be included for each cohort.
- Incidence of TEAEs related to APX005M will be tabulated by PT and maximum CTCAE grade, in order of highest number of subjects. A table will be included for each cohort.

### **TEAEs: Worst grade by subject related to Radiotherapy (only cohort 3)**

- Incidence of TEAEs related to radiotherapy will be tabulated by SOC, PT and maximum CTCAE grade, showing the total incidence of SOC and PT within SOC.
- Incidence of TEAEs related to radiotherapy will be tabulated by PT, and maximum CTCAE grade, in order of highest number of subjects.

### **TEAEs: Leading to treatment discontinuation (by cohort)**

- Incidence of TEAEs leading to treatment discontinuation will be tabulated by SOC and PT and cohort, showing the total incidence of SOC and PT within SOC.
- Incidence of TEAEs leading to treatment discontinuation will be tabulated by PT and cohort in order of highest number of subjects.

### **TEAEs: Worst grade by subject Immune mediated:**

- Incidence of TEAEs immune mediated will be tabulated by SOC, PT and maximum CTCAE grade, showing the total incidence of SOC and PT within SOC.
- Incidence of TEAEs immune mediated will be tabulated by PT and maximum CTCAE grade, in order of highest number of subjects.

### **TEAEs: Worst grade by subject of symptoms that compromise an APX005M Infusion reaction and/or cytokine release syndrome:**

- Incidence of TEAEs considered symptoms that compromise an APX005M infusion reaction and/or cytokine release syndrome will be tabulated by SOC, PT and maximum CTCAE grade, showing the total incidence of SOC and PT within SOC.
- Incidence of TEAEs considered symptoms that compromise an APX005M infusion reaction and/or cytokine release syndrome will be tabulated by PT and maximum CTCAE grade, in order of highest number of subjects.

### **Serious Adverse events (by cohort):**

- Incidence of SAEs will be tabulated by SOC, PT and cohort, showing the total incidence of SOC and PT within SOC.
- Incidence of SAEs will be tabulated by PT and cohort, in order of highest number of subjects.

### **Serious Adverse events related to APX005M (by cohort):**

- Incidence of SAEs related to APX005M will be tabulated by SOC, PT and cohort, showing the total incidence of SOC and PT within SOC.
- Incidence of SAEs related to APX005M will be tabulated by Preferred Term (PT) in order of highest number of subjects.

### **Adverse events with fatal outcome (by cohort):**

- Incidence of TEAEs with fatal outcome will be tabulated by SOC, PT and cohort, showing the total incidence of SOC and PT within SOC.
- Incidence of TEAEs with fatal outcome will be tabulated by Preferred Term (PT) in order of highest number of subjects.

### 5.3.3.3 Deaths

The primary cause of death will be described for safety population (Death due to disease / Death due to AE / Death, cause unknown / Other).

A listing of deaths will be provided.

### 5.3.3.4 Clinical Laboratory Evaluation

To evaluate the safety profile the following laboratory tests will be performed locally:

- Serum chemistry
- Hematology
- Coagulation
- Urinalysis
- Pregnancy.

For each quantitative laboratory parameter, the values, and changes from baseline will be summarized (including number, mean, SD, median, Q1, Q3, minimum, and maximum) will be calculated for each visit or study assessment by cohort.

The frequency of subjects with clinically significant abnormal laboratory values will be tabulated for baseline and each scheduled post baseline visit, by cohort and overall.

The shift tables for baseline versus all visits will be presented for all chemistry and hematology laboratory parameters based on categories of below, within and above normal range.

Lab Original results with ND/ NA/ NE/ UNK/ NQ/ UN etc: will not be evaluated or used for the analysis purpose.

All serum chemistry, hematology, coagulation, and urinalysis data will be listed by subject; the clinically significant abnormal values will be flagged.

Notes:

- Clinical laboratory data will be analysed using standardized values.
- Repeated or unscheduled tests will not be summarized for each scheduled visit but will be included in the listing.
- The tables will include the visits until the number of patients will be representative.
- Only evaluable data will be used, and missing data will not be imputed.

The pregnancy results will also be listed only.

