4.1.2.5 Cycles 3+ Optional Safety Visit

- Collect vital signs
- Laboratory evaluations:
 - 1) Serum chemistry
 - 2) Hematology
- Record AEs and ConMeds

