4.3 Efficacy Assessments

Tumor assessment will be performed within 21 days prior to start of investigational therapy and during the Treatment Period (every 8 ± 1 week). Subject that discontinue treatment before the first scheduled on study tumor assessment (8 weeks following the first dose of APX005M) should have the tumor response evaluated at the end of treatment visit. Tumor assessments will follow RECIST 1.1 guidelines. Complete or partial responses should be confirmed at a subsequent time point 4 weeks later.

Subjects enrolled in Cohort 3 are required to have a minimum of 3 measurable target lesions. The lesions which are the first and second radiation therapy targets should be recorded.

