4.3.2 Modified RECIST 1.1 for Immune-based Therapeutics

Accumulating evidence indicates that patients with solid tumors treated with immunotherapy may derive clinical benefit despite initial evidence of PD. For the purpose of establishing the Phase 2 secondary endpoint the iRECIST (modified RECIST 1.1 for immune-based therapeutics [22]) will be used to assess tumor response for all treated subjects.

Subjects with RECIST 1.1-defined PD (iUPD [iRECIST]) should have a repeated tumor assessment 4-8 weeks later in order to confirm PD and will be permitted to continue treatment as long as they meet the criteria in [Section 3.2.6.2](#) and they do not have confirmed PD as defined by iRECIST. Subjects that are deemed clinically unstable are not required to have repeat imaging for confirmation of PD.

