#### 5.3.3.4.1 Selected laboratory parameters

Selected laboratory parameters will be graded according to CTCAE Version 4.03, the worst CTCAE grade will be summarized. All values will be considered, regardless of whether it is considered clinically significant or not.

For each test, subjects will be characterized based on their worst severity grade observed during on treatment period.

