**Note:**

Repeated or unscheduled tests will be considered in calculating this information.

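### For 24 of 33 laboratory analytes, abnormalities found only at unscheduled draws reach no laboratory summary table, so the lab tables can understate them and disagree with the adverse event tables

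*SAP*

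**What the plan says.** SAP 5.3 sets a general rule: "Unscheduled or repeat assessments will not be included in summary tables but will be included in listings". It names no exception.

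SAP 5.3.3.4 applies the rule to laboratory data. On abnormalities it says: "The frequency of subjects with clinically significant abnormal laboratory values will be tabulated for baseline and each scheduled post baseline visit". On off-schedule tests it says: "Repeated or unscheduled tests will not be summarized for each scheduled visit but will be included in the listing". Shift tables are planned for chemistry and hematology but not for coagulation. All results are listed, with clinically significant values flagged.

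SAP 5.3.3.4.1 takes the opposite approach for selected parameters. It summarizes the worst CTCAE grade in the on-treatment period: "All values will be considered, regardless of whether it is considered clinically significant or not". The notes to the hematology and chemistry tables both say: "Repeated or unscheduled tests will be considered in calculating this information".

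On the protocol side, Section 2.2 leaves safety visits within a cycle to clinical need after Cycle 2. Section 4.1.2.5 provides a "Cycles 3+ Optional Safety Visit" with chemistry and hematology. Section 4.2.6.3 requires INR at screening only, and asks for D-dimer (where the local laboratory offers it) at baseline and on Day 8 of Cycles 1 and 2. Later tests of either are made only when clinically indicated.

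**The concern.** An unscheduled laboratory test is usually ordered because someone suspects a problem. Leaving such tests out of by-visit means is normal practice, since it keeps one value per subject per visit. Leaving them out of a count of subjects with abnormal results is different, because the omitted values are the ones most likely to be abnormal.

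Protocol 6.3 lists graded laboratory abnormalities and changes from baseline in laboratory results among the secondary endpoints. If the SAP is followed as written, a clinically significant creatinine rise found between doses in a later cycle would be missing from the lab tables. The same event should appear in the adverse event tables, because Protocol 5.3.8 requires clinically significant laboratory values to be reported there. A reader of the study report would then see two safety summaries that disagree, with nothing to explain why.

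**Working it through.** The plan states no figure on this point, so the check is a count of analytes and a comparison of tables.

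**Step 1. Analytes collected** (Protocol 4.2.6.2, which also holds the hematology list, and 4.2.6.3)
- Chemistry: 19
- Hematology: 10 (hemoglobin, hematocrit, white cells, five differential counts, red cells, platelets)
- Coagulation: 4 (PT, aPTT, INR, D-dimer)
- Total: 19 + 10 + 4 = 33

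**Step 2. Analytes with a worst-grade table that uses unscheduled tests** (SAP 5.3.3.4.1.1 and 5.3.3.4.1.2)
- Hematology: white cells, neutrophils, platelets, lymphocytes, hemoglobin = 5
- Chemistry: AST, ALT, total bilirubin, alkaline phosphatase = 4
- Coagulation: 0
- Total: 5 + 4 + 0 = 9. The Hy's law display combines AST, ALT and bilirubin and adds no analyte.

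**Step 3. Analytes without one**

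| Panel | Collected | Covered | Not covered |
|---|---|---|---|
| Chemistry | 19 | 4 | 15 |
| Hematology | 10 | 5 | 5 |
| Coagulation | 4 | 0 | 4 |
| Total | 33 | 9 | 24 |

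24/33 = 72.7% of analytes overall, and 15/19 = 78.9% of the chemistry panel.

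**Step 4. Where an off-schedule value can appear after Cycle 2.** Take a clinically significant creatinine value at an unscheduled draw in Cycle 4, with acceptable values on Day 1 of Cycles 4 and 5.
- Clinically significant abnormality table: scheduled visits only, so not counted.
- Change-from-baseline and shift tables: off-schedule tests excluded by SAP 5.3 and the note in 5.3.3.4, so not counted.
- Worst-grade table: creatinine is not included.
- Listing: shown and flagged.
- TEAE tables: counted, if reported as Protocol 5.3.8 requires.

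If the draw was made at the Cycle 3+ optional visit, the result depends on whether that visit counts as scheduled. The SAP does not say.

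**Step 5. Coagulation.** After screening, an INR value can come only from a clinically indicated test. The same holds for D-dimer after Cycle 2 Day 8. These values are unscheduled by design, and coagulation has neither a shift table nor a worst-grade table. Protocol 1.2.4 names thromboembolic events as a rare possible risk.

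**Step 6. Size per missed subject**, using the planned cohort sizes in SAP 5.1: 1/11 = 9.1% in Cohorts 1 and 2, and 1/18 = 5.6% in Cohort 3. The documents do not say how many off-schedule abnormalities to expect.

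**The case against.** The strongest reply is that the important signals are already covered. The transient changes described in Protocol 1.2.4 in routine panel tests are in transaminases, bilirubin, lymphocytes and platelets, and all of these have worst-grade tables that include unscheduled tests. Protocol 5.3.8 sends any clinically significant laboratory value to the adverse event form, whatever the visit, and TEAEs are tabulated by term and grade. Several of the 24 analytes add little; hematocrit and red cell count, for example, largely follow hemoglobin. All of this stands and keeps the point modest. It does not explain why a table headed clinically significant abnormalities should omit some of them, nor does it cover creatinine, INR or D-dimer within the lab tables.

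Two stronger readings are tempting, and the documents support neither.

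- A reader might infer that after Cycle 2 laboratory abnormalities are tabulated only from recovered, pre-dose values. The nine analytes above contradict this. So do the End of Treatment and second-biopsy draws (Protocol 4.1.2.8 and 4.1.2.7), which are not pre-dose. The retreatment limits in Protocol 3.2.4 (ANC at least 1,000 and WBC at least 2,000 per mm³) also admit values that are Grade 2 in SAP Table 8.
- A reader might infer that SAP 5.3 bars confirmatory scans from the response tables. Protocol 4.3 says: "Complete or partial responses should be confirmed at a subsequent time point 4 weeks later". A week 8 response would then be confirmed at week 8 + 4 = 12, between the scan windows of weeks 7–9 and 15–17. Protocol 4.3.2 says that subjects with RECIST 1.1 progression "should have a repeated tumor assessment 4-8 weeks later in order to confirm PD". But SAP 4.4.1 and 4.4.2 set eligibility for best response by date and not by schedule. They require confirmation, and they allow best response to be confirmed in follow-up. SAP Table 7 likewise relies on confirmation of progression at the next assessment. No text excludes these scans, and nothing shows that a responder would be lost.

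**Conclusion.** The point holds for laboratory summaries. For 24 of 33 analytes, an abnormality found only at an unscheduled or clinically indicated draw is left out of every laboratory summary table. This matters most after Cycle 2, when scheduled sampling thins out, and most clearly for INR and D-dimer. The lab tables can understate these abnormalities and differ from the TEAE tables.

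The number of subjects affected is unknown, and each one moves a cohort's rate by 5.6 or 9.1 percentage points. The conclusion assumes that SAP 5.3 and 5.3.3.4 are applied as written and, for chemistry and hematology, that the optional visit is not treated as scheduled or the draw falls outside it. Adverse event reporting limits the harm without removing it.

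There is also a conflict of wording: the unqualified rule in SAP 5.3 contradicts the notes to the worst-grade tables. For tumor assessments, the same rule needs clarification only. The primary endpoint, the sample size and the stated standard errors are unaffected.

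**What to change.** 1. In SAP 5.3.3.4, add one per-subject row to the clinically significant abnormality table for every laboratory parameter: *any post-baseline value, including unscheduled, repeat and optional-visit tests*. This works however the optional visit is classified.
2. In SAP 5.3, limit the exclusion of unscheduled and repeat assessments to by-visit summaries, so that it agrees with the notes in 5.3.3.4.1.1 and 5.3.3.4.1.2.
3. In the same place, state as a clarification that tumor assessments follow the best overall response rules in SAP 4.4.1 and 4.4.2, whether or not they fall on the 8-week schedule.

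The cost is one table row per parameter and a short addition to the SAP text. No new data are needed, since the values are already collected and listed. Reported rates of laboratory abnormality may rise slightly.
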